## **5. STUDY INTERVENTIONS**

### **5.1 Tai Chi**

To ensure that our intervention was developed thoughtfully, we adapted the framework proposed by [name] for developing yoga interventions, which recommends specification of style of practice, dose and delivery format, components of the

intervention, specific class sequences, use of modifications, selection and training of instructors, home practice facilitation, and intervention fidelity. For this feasibility RCT, treatment protocols were developed for both standard Tai Chi and for a maintenance period wherein the protocol is tapered. The treatment components are outlined below, with further details given in the study protocol along with items to be developed. The intervention includes strategies for ensuring intervention fidelity (i.e., “the extent to which core components of interventions are delivered as intended by the protocols”), because it is essential for accurately interpreting treatment effects. The Treatment Fidelity Workgroup of the NIH Behavior Change Consortium (BCC) developed recommendations for incorporating strategies for monitoring and enhancing treatment fidelity in behavioral interventions. Many are relevant for Tai Chi. Many of these recommendations are covered in [name]’s framework (i.e., provider training, treatment delivery, treatment receipt) but we will ensure the other relevant recommendations are all incorporated into our trial, as described below.

### **5.1.1 Documentation of the Enhanced Tai Chi Treatment Protocol**

The Tai Chi consultants developed a detailed Tai Chi intervention manual. It includes the lesson plans for each class (including a description of the key features and photos and suitable visual imagery).

The latter will be supplemented with a teacher training manual, containing the most effective strategies for ensuring treatment fidelity, the minimum qualifications for Tai Chi instructors, how they will be recruited, trained on the study protocol, tested and monitored for adherence to the protocol, and how their skills will be maintained during the study period. This manual will include all study materials given to participants (e.g., hard copy or DVD descriptions of the movements they are learning), and checklists for evaluating instructor adherence to the treatment protocol.

### **5.1.2 Standard Tai Chi Protocol for cLBP**

Our Standard Tai Chi intervention will include group classes – each 60 minutes – of Yang style Tai Chi twice week for 12 weeks. We chose to use the Yang style because it is the most popular form of Tai Chi worldwide, can be delivered in a simple format that is easily replicated, has been used in numerous RCTs and is known effective for falls prevention. Twelve weeks of twice-weekly classes is the most commonly used dose of Tai Chi in RCTs and has proved practical for older adults in other studies. Therefore, this should be sufficient instruction to understand the fundamentals and practice safely. Consultant Tai Chi instructor [name] and Tai Chi researcher [name], who each have over 35 years of Tai Chi training and teaching experience, developed the Tai Chi intervention based on their prior experience with this population. Guided by the literature on beneficial treatments for chronic pain, classes will include the following components: simple classical Tai Chi movements to enhance musculoskeletal strength and flexibility, efficient posture, heightened body awareness, mindful diaphragmatic breathing, and healing imagery and visualization. In addition, by using a class format, psychosocial interaction can be enhanced. All movements were designed to assure safety and emphasize those that are most relevant to persons with cLBP.

In both cohorts, the first class will begin with a short introduction to Tai Chi principles, an overview of the class format and curriculum, and expectations regarding home practice. All subsequent classes will include an initial check-in period to discuss any questions or concerns related to prior classes and/or home practice. Formal Tai Chi instruction will begin with a focus on posture and abdominal breathing followed by basic Tai Chi warm-up exercises to loosen up the physical body, reinforce Tai Chi principles of incorporating mindfulness and imagery into movement, promote overall relaxation, and generating awareness of efficient breathing. The centerpiece of the protocol will include six Tai Chi movement flows over the course of the 12 weeks: ‘opening move: step out, raise and lower arms’; ‘grasping sparrow’s tail on the left side; ‘grasping sparrow’s tail on the right side’; ‘single whip’, ‘cloud hands’; ‘repeat of single whip’, ‘step back, lower arms’. Classes will end with a closing and centering breathing exercise. These movements will be progressively added to the warm-up and cool down exercises over the 12 week intervention (i.e., movement 1 introduced during week 1; movements 2 and 3 during weeks 2-5; and the remaining movements during weeks 6-10). The class format for each week is shown below.

**Table 1. Standard Tai Chi Class Format: Proposed Version**

Week	PROPOSED Class Format
1	
 
1. Introduction & Overview of Tai Chi program (5 min) (1st class) and Greetings & Discussion of Home Practice Efforts (5 min) (2nd class)
 
2. Explanation of Basics: Posture, Breathing, Mental State (5 min)
 
3. Introduction of Relaxation Sequence, Breathing & Standing Meditation (10 min)
 
4. Warm-up Exercises: #1 (10 min)
 
5. Learn Movement #1: Opening Move: Step Out, Raise and Lower Arms (10 Min)
 
6. Student Practice & Individual Correction/Modification (10 min)
 
7. Closing, Centering Breath & Visualization of Movement (3 min)
 
8. Q & A (5 min)
 
9. Review Homework assignment: Relax & Check Posture; Warm-up #1 & Movement #1 (2 min)
 

2	
 
1. Greetings & Discussion of Home Practice Efforts (5 min)
 
2. Review of Basics: Posture, Breathing & Mental State (5 min)
 
3. Relaxation Sequence, Breathing & Standing Meditation (5 min)
 
4. Warm-up Exercises #1 & 2 (10 min)
 
5. Repeat/Practice/ Correct/Modify Movement Flow #1 (5 min)
 
6. Learn Movement Flow #2, Element #1: Ward Off Left (10 min)
 
7. Student Practice Movement Flows #1&2 (Element #1), Individual Corrections/Modifications (10 min)
 
8. Closing, Centering Breath & Visualization of Movement (3 min)
 
9. Q & A (2 min)
 
10. Review Homework assignment: Relax & Check Posture; Warm-up #1 & 2 & Movement #1 & 2, element #1 (5 min)
 

3	
 
1. Greetings & Discussion of Home Practice Efforts (5 min)
 
2. Relaxation Sequence, Breathing & Standing Meditation (5 min)
 
3. Warm-up Exercises #1,2,3 (10 minutes)
 
4. Repeat/Practice/ Correct/Modify previous Movement flows (10 min)
 
5. Learn Movement Flow #2, Element #2, Grasping Sparrow's Tail: Roll Back, Press & Push (10 min)
 
6. Student Practice & Individual Correction/Modification (10 min)
 
7. Closing, Centering Breath & Visualization of Movement (3 min)
 
8. Q& A (2 min)
 
9. Review Homework assignment: Relax & Check Posture; Warm-up #1 & 2 & Movement #1 & 2 (entire) (5 min)
 

4	
 
1. Greetings & Discussion of Home Practice Efforts (5 min)
 
2. Relaxation Sequence, Breathing & Standing Meditation (5 min)
 
3. Warm-up Exercises #2,3,4 (10 min)
 
4. Repeat/Practice/ Correct/Modify Previous Movement Flows (10 min)
 
5. Learn Movement Flow #3, Transition & Grasping Sparrow's Tail, right side; (10 min)
 
6. Student Practice & Individual Correction/Modification (10 min)
 
7. Closing, Centering Breath & Visualization of Movement (3 min)
 
8. Q& A (2 min)
 
9. Review Homework assignment: Relax & Check Posture; Warm-up #2,3,4; Movement #1,2 & 3 (5 min)
 

5	
(Repeat Week #4)
 
 
1. Greetings & Discussion of Home Practice Efforts (5 min)
 
2. Relaxation Sequence, Breathing & Standing Meditation (5 min)
 
3. Warm-up Exercises #2,3,4 (10 minutes)
 
4. Repeat/Practice/ Correct/Modify Previous Movement Flows (10 min)
 
5. Review Movement Flow #3, Transition & Grasping Sparrow's Tail, right side; (10 min)
 
6. Student Practice & Individual Correction/Modification (10 min)
 
7. Closing, Centering Breath & Visualization of Movement (3 min)
 
8. Q& A (2 min)
 
9. Review Homework assignment: Relax & Check Posture; Warm-up #2,3,4; Movement #1,2 & 3 (5 min)
 

6	
 
1. Greetings & Discussion of Home Practice Efforts (5 min)
 
2. Relaxation Sequence, Breathing & Standing Meditation (5 min)
 
3. Warm-up Exercises #2,3,4 & 5 (10 minutes)
 
4. Repeat/Practice/Correct/Modify Previous Movement Flows (10 min)
 
5. Learn Movement Flow #4, Single Whip (10 min)
 

	
6. Student Practice & Individual Correction/Modification (10 min)
 
7. Closing, Centering Breath & Visualization of Movement (3 min)
 
8. Q& A (2 min)
 
9. Review Homework assignment: Relax & Check Posture; Warm-up #2,3,4; Movement #1,2,3 & 4 (5 min)

7	
(Repeat Week #6)
 
1. Greetings & Discussion of Home Practice Efforts (5 min)
 
2. Relaxation Sequence, Breathing & Standing Meditation (5 min)
 
3. Warm-up Exercises #2,3,4 & 5 (10 min)
 
4. Repeat/Practice/Correct/Modify Previous Movement Flows (10 min)
 
5. Review Movement Flow #4, Single Whip (10 min)
 
6. Student Practice & Individual Correction/Modification (10 min)
 
7. Closing, Centering Breath & Visualization of Movement (3 min)
 
8. Q& A (2 min)
 
9. Review Homework assignment: Relax & Check Posture; Warm-up #2,3,4,5; Movement #1,2,3 & 4 (5 min)

8	
1. Greetings & Discussion of Home Practice Efforts (5 min)
 
2. Relaxation Sequence, Breathing & Standing Meditation (5 min)
 
3. Warm-up Exercises #2,3,4 & 5 (10 minutes)
 
4. Repeat/Practice/Correct/Modify Previous Movement Flows (10 min)
 
5. Learn Movement Flow #5, Cloud Hands & Repeat Single Whip (10 min)
 
6. Student Practice & Individual Correction/Modification (10 min)
 
7. Closing, Centering Breath & Visualization of Movement (3 min)
 
8. Q& A (2 min)
 
9. Review Homework assignment: Relax & Check Posture; Warm-up #2,3,4, 5; Movement #1,2,3,4, 5& 4 (5 min)

9	
(Repeat Week #8)
 
1. Greetings & Discussion of Home Practice Efforts (5 min)
 
2. Relaxation Sequence, Breathing & Standing Meditation (5 min)
 
3. Warm-up Exercises #2,3,4 & 5 (10 minutes)
 
4. Repeat/Practice/Correct/Modify Previous Movement Flows (10 min)
 
5. Learn Movement Flow #5, Cloud Hands & Repeat Single Whip (10 min)
 
6. Student Practice & Individual Correction/Modification (10 min)
 
7. Closing, Centering Breath & Visualization of Movement (3 min)
 
8. Q& A (2 min)
 
9. Review Homework assignment: Relax & Check Posture; Warm-up #2,3,4, 5; Movement #1,2,3,4, 5, & 4 (5 min)

10	
 
1. Greetings & Discussion of Home Practice Efforts (5 min)
 
2. Relaxation Sequence, Breathing & Standing Meditation (5 min)
 
3. Warm-up Exercises, Choose from: #1-6 (10 min)
 
4. Repeat/Practice/Correct/Modify Previous Movement Flows (10 min)
 
5. Learn Movement Flow #6, Cross Hands, Close (10 min)
 
6. Student Practice & Individual Correction/Modification (10 min)
 
7. Closing, Centering Breath & Visualization of Movement (3 min)
 
8. Q& A (2 min)
 
9. Review Homework assignment: Relax & Check Posture; Warm-up #2,3,4, 5; Movement #1,2,3,4,5, 4 &6 (5 min)
 

11	
 
1. Greetings & Discussion of Home Practice Efforts (5 min)
 
2. Relaxation Sequence, Breathing & Standing Meditation (5 min)
 
3. Warm-up Exercises, Choose from: #1-6 (10 min)
 
4. Review entire sequence (15 min)
 
5. Student Practice & Individual Correction/Modification (15 min)
 
6. Closing, Centering Breath & Visualization of Movement (3 min)
 
7. Q& A (2 min)
 
8. Review Homework assignment: Relax & Check Posture; Warm-ups 1-6, Entire Flow Sequence (5 min)
 

12	(Repeat Week #11) 
 
1. Greetings & Discussion of Home Practice Efforts (5 min)
 
2. Relaxation Sequence, Breathing & Standing Meditation (5 min)
 
3. Warm-up Exercises, Choose from: #1-6 (10 min)
 
4. Review entire sequence (15 min)
 
5. Student Practice & Individual Correction/Modification (15 min)
 
6. Closing, Centering Breath & Visualization of Movement (3 min)
 
7. Q& A (2 min)
 
8. Review Homework assignment: Relax & Check Posture; Warm-ups 1-6, Entire Flow Sequence (5 min)
 

In each class, modifications will be employed as necessary for participants who have physical limitations. The most common modifications are reducing slightly the depth of the postural stance due to knee pain and lowering the height of the arms due to shoulder issues. However, we will take note of all physical issues and see whether the protocol should be modified or additional modifications should be recorded as part of the protocol finalization for the full-scale trial.

The Tai Chi classes will be offered in large, quiet classrooms at Kaiser Permanente Washington facilities that are centrally located and that provide easy access for persons with physical limitations. We have successfully used such classrooms in previous studies.

Study participants who are randomized to the Tai Chi intervention will be asked to practice at home on all non-class days for 15 minutes. The home practice assignments are shown in Table 2. We will prepare home practice aides to assist with this (e.g., videos with the sequences available on Youtube or a DVD).

**Table 2. Home Practice Assignments**

Week(s)	Home Practice Assignment
1	Relax & Check Posture; Warm-up #1 & Movement #1
2	Relax & Check Posture; Warm-up #1 & 2 & Movement #1 & 2, element #1
3	Relax & Check Posture; Warm-up #1 & 2 & Movement #1 & 2 (entire)
4, 5	Relax & Check Posture; Warm-up #2,3,4; Movement #1,2 & 3
6 & 7	Relax & Check Posture; Warm-up #2,3,4, 5; Movement #1,2,3 & 4
8 & 9	Relax & Check Posture; Warm-up #2,3,4,5; Movement #1,2,3,4, 5 & 4
10	Relax & Check Posture; Warm-up #2,3,4, 5, 6; Movement #1,2,3,4,5, 4 & 6
11&12	Relax & Check Posture; Warm-ups 1-6, Entire Flow Sequence

### **5.1.3 Maintenance Tai Chi Protocol for cLBP**

A key feature of receiving benefits from mind-body interventions like Tai Chi is the probable need to continue regular practice in order to continue receiving their benefits. Consequently, investigation of strategies for maintenance of long term practice is important. We will therefore investigate a suite of strategies for achieving this goal. We have adopted ideas from the health promotion literature as well as from the chronic pain literature. We plan to investigate the value of adding additional classes at the end of the primary intervention period. By tapering class frequency over the course of an additional 24 weeks, we can investigate whether such a strategy is practical, leading to better maintenance of a Tai Chi practice over the longer term and therefore improving back function, pain, balance, mood and overall quality of life. During this maintenance period, we propose 6 weeks of weekly classes, 6 weeks of classes every other week (i.e., 3 classes) and 12 weeks of monthly classes (i.e., 3 classes) to offer a high enough dose to encourage long term maintenance. Classes will be 60 minutes as in the Standard Tai Chi protocol and will include the movement flows and as well as the other components that were part of the Standard Tai Chi classes. Participants will be asked to practice at home for 15-minutes on all non-class days.

The Tai Chi classes will be offered in large, quiet classrooms at Kaiser Permanente Washington facilities that are centrally located and that provide easy access for persons with physical limitations. We have successfully used such classrooms in previous studies.

#### **5.1.4 Selection and training of instructors**

Tai Chi consultant [name] will teach the classes for our two Tai Chi cohorts. She is exceptionally experienced with over 35 years of practicing Tai Chi and has run a successful Tai Chi school in Seattle for over 20 years. In a future trial, we will require all instructors to have a minimum of 10 years of practice of Yang style Tai Chi, have taught for at least seven years with five years of experience teaching seniors, have current CPR certification and be willing to adhere to our study protocol. In addition, we will require an in-person demonstration to ensure that they have relevant mastery of Yang style Tai Chi, general teaching competence, comfort giving verbal instruction, flexibility in teaching style and excellent interpersonal dynamics. The demonstration will include evaluation of their own Yang style form as well as their ability to instruct others in warm-ups and selected tai chi flows that are relevant to this protocol. In addition, they will attend our in-person teacher training, which will include an introduction to the study design and participant inclusion and exclusion criteria, an in depth discussion of the protocol, with practice teaching for consistency among instructors and special issues that may arise in this population. Because [name] is very well connected with the Seattle tai chi community, she will be able to easily recruit instructors who are likely to be successful as instructors in this study. If additional instructors are necessary for this feasibility study, [name] will train them.

#### **5.1.5 Home practice facilitation**

We will supplement classes with 15-minutes of home practice on several non-study days and practice incorporating Tai Chi principles into life. We will use Youtube videos and if requested, DVDs to guide the participant through the movement flows. Home practice logs will be used to track home practice, a strategy we have used with some success in prior studies. Results from our pilot study of using an iPad app designed to enhance adherence to exercise found that it was not easy for study participants to use.

#### **5.1.6 Intervention fidelity:**

##### **i. Class protocol**

For this feasibility study, Research Specialists who staff the classes will complete intervention fidelity checklists at all classes. [name], who has developed familiarity with the Tai Chi protocol during the development of the intervention manual, will attend two randomly selected classes in each of the class series to ensure the instructor is adhering to the protocol. She will note all observed protocol violations, both errors of omission and commission on the checklists developed for this purpose. [name] will also be in weekly contact with [name] during each class series to ensure any questions or concerns are quickly identified and resolved (Consultant [name] will be brought in if necessary). We will focus on the suitability of these procedures for a larger study and to making any necessary modifications.

##### **ii. Optimizing treatment dose**

Tai Chi requires some focused attention to learn the fundamentals undergirding this mind-body therapy and requires continued practice in order to maintain benefits.. Participants will receive a reminder call before the first class and whenever they miss any classes.. During each class, participants will be reminded of the importance of attending classes and of practicing at home. A portion of each class will be devoted to answering questions that arise during home practice and, if necessary, to exploring any perceived barriers to adherence. Research Specialists will take attendance at each class.

### **iii Develop strategies to assess participants' understanding of intervention and ability to engage in Tai Chi**

We will evaluate several methods to assess the extent to which participants feel comfortable and understand the techniques they are being taught and their confidence in performing them in class and practicing them at home. This will include having a Research Specialist observe each class and note any observed difficulties (as well as corrections given by Instructor [name]), asking about these issues on our follow-up questionnaires, and possibly having another Tai Chi instructor observe and rate each participant's movements during classes (e.g., unable to perform movements, low/moderate/high skill in performing the movements).

### **iv. Documentation of intervention fidelity**

In addition to identifying any general problems with our implementation procedures or with specific aspects of the treatment protocols, we will determine the level of adherence to class attendance and home practice in the standard and maintenance time periods. Class attendance will be documented by a Research Specialist who will attend all of the classes to manage study-related processes and allow the Tai Chi instructor to pay full attention to her students. We will also collect data from students on home practice. At the first class, we will give participants weekly logs to record their home practice throughout the 36-week intervention period (We will ask that they bring their logs to class once a week and to give them to the Research Specialist). We have used this process in our recent yoga RCT with moderate success. In addition, we will ask participants during the 12, 26 and 52-week follow-up interviews about the number of days they practiced during the prior week and the average number of minutes they practiced on those days. This method of collecting data on home practice has worked well in our previous RCTs. Finally, we will assess treatment fidelity by reviewing the information we collected evaluating the ability of the Tai Chi instructor to adhere to the treatment protocols and the extent to which participants were able to grasp what they were taught and translate it into skillful Tai Chi movements.

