**Figure: Anticipated Design of Full-scale Trial**

### **3. STUDY DESIGN**

The feasibility study will be a three arm parallel group RCT comparing Enhanced Tai Chi to Comprehensive Health Education (Attention Control) to Usual Medical Care in older adults (65 years and older) with cLBP. We plan to recruit 78 community-dwelling, older adults from Kaiser Permanente Washington, an integrated healthcare system with a large population of Medicare enrollees and from the general population as necessary. We will randomize eligible and willing individuals in a 8:3:5 ratio to Enhanced Tai Chi (n=39), Attention Control (n=15) and Usual Medical Care (n=24) using a computer with a tamperproof program that is not predictable in advance. Participants in the Enhanced Tai Chi will receive 36 weeks of classes (which will be 60 minute classes for 2x/week for 12 weeks; followed by a maintenance schedule of 60 minutes classes 1x/week for 6 weeks, then 60 minute classes every 2 weeks for 6 weeks and then 60 minute classes every 4 weeks for 12 weeks. Participants will be asked to practice at home for 15 minutes on every non-class day. They will be provided with YouTube video access (and, if desired, DVDs), and handouts to assist with this.). All classes will be taught in a Kaiser Permanente Washington classroom. Data on adherence to Tai Chi classes and home practice will be collected during the classes themselves. Because Tai Chi will be taught as a series of progressive classes, participants will be recruited in two cohorts of 32 each; each class of Tai Chi will consist of 16 participants.

Outcome assessments will be collected at baseline, 12, 26, and 52 week during in-person visits. Outcome assessors will be unaware of any participant's study groups,

but participants will be asked to complete their own questionnaires. They will either complete them on paper forms or using a tablet computer designed to minimize errors.

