### **9.6 Data Analyses**

#### **i. Feasibility of a full-scale RCT**

We will use descriptive analyses to examine many aspects of feasibility, including recruitment, randomization, Tai Chi adherence, adverse events and follow-up rates. To assess recruitment feasibility, we will collect information at every stage of our recruitment and randomization process. We will compute the rates of screening and enrollment per month. This will let us know how many invitation letters we would need to send to potentially eligible persons to meet recruitment goals in a large RCT. Our primary method of recruitment will be through mailed invitations to persons meeting our initial inclusion and exclusion criteria according to the information in the EMR (see sections 4.2 and 4.3). This recruitment method will allow us to calculate the percentage of these potentially eligible persons who end up agreeing to participate in the trial. Because ICD codes do not distinguish between chronic and acute pain and do not always distinguish between pain in the lumbar spine (low back) from pain in mid-back or neck, most potentially-eligible persons will be found during screening interviews to not have cLBP. This information will help determine the number of recruitment sites that would be necessary to conduct an adequately-powered RCT. If our primary recruitment method proves inadequate for efficiently meeting our goals, we will evaluate the ability of alternative methods determined in the Administrative Year (e.g., advertising in the health plan's quarterly magazine) to accrue significant numbers of additional participants.

To assess RCT retention rates, we will compute the treatment specific retention rates, which are typically large in our trials. For Tai Chi treatment adherence, we will compute the number of classes attended and the amount of home practice per week. Benchmarks for Tai Chi adherence will be derived (in the Administrative Year) by a thorough literature review of adherence in RCTS evaluating exercise for cLBP, Tai Chi for chronic pain and Tai Chi in the elderly. Additional information, such as ratings of how well participants perform key aspects of the Tai Chi protocol, will be obtained.

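### Home-practice logs are collected only at class, so log return depends on attendance; weekly hand-in cannot be followed in half of the maintenance weeks, and no rule covers unreturned logs

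*Protocol*

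**What the plan says.** Protocol 5.1.6.iv: "we will give participants weekly logs to record their home practice throughout the 36-week intervention period". It then says: "We will ask that they bring their logs to class once a week and to give them to the Research Specialist". Section 3 agrees: "Data on adherence to Tai Chi classes and home practice will be collected during the classes themselves". Table 4 (Schedule of Evaluations) marks the logs in the class column only, not at the 12/26-week or 52-week visits.

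The class schedule is in 5.1.2 ("Yang style Tai Chi twice week for 12 weeks") and 5.1.3. The latter first says "we propose 6 weeks of weekly classes", then "6 weeks of classes every other week (i.e., 3 classes) and 12 weeks of monthly classes (i.e., 3 classes").

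Section 5.1.6.iv also provides a second source: at the 12-, 26- and 52-week follow-ups, participants are asked on how many days they practised in the prior week and for how many minutes on average. Table 5 lists this item at the same three times.

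For analysis, Protocol 9.6.i and the SAP (Data Analyses) say the same thing: "we will compute the number of classes attended and the amount of home practice per week". Neither says which source supplies the figure, who is in the denominator, or what happens to logs not returned.

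**The concern.** Home-practice adherence is a named feasibility outcome in both the primary and the secondary treatment period (Precis, Feasibility Outcomes 2 and 3). A log that can be returned only by coming to class is most likely to be missing for people who have stopped coming. Those people may well practise less at home, although the documents do not say so. A summary of the returned logs would then describe attenders, not the 39 people to be randomised to Tai Chi.

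The taper adds a second difficulty. Once classes drop to every other week and then monthly, the weekly hand-in instruction cannot be carried out, and it is the maintenance period that Aim 3 asks about. Protocol 9.6.i intends to judge Tai Chi adherence against literature benchmarks, so a shift in the reported level could change how adherence is read.

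**Working it through.** **1. Length of the log period.** From 5.1.2 and 5.1.3: 12 + 6 + 6 + 12 = 36 weeks, which matches the 36 weeks in 5.1.6.iv.

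**2. Weeks with a class.**

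| Phase | Weeks | Length in weeks | Classes | Weeks with a class | Weeks without |
|---|---|---|---|---|---|
| Standard, twice weekly | 1-12 | 12 | 24 | 12 | 0 |
| Maintenance, weekly | 13-18 | 6 | 6 | 6 | 0 |
| Maintenance, every other week | 19-24 | 6 | 3 | 3 | 3 |
| Maintenance, monthly | 25-36 | 12 | 3 | 3 | 9 |
| Total | 1-36 | 36 | 36 | 24 | 12 |

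Weekly hand-in is impossible in 12/36 = 33% of log weeks. All 12 are maintenance weeks (12/24 = 50%), and all lie in the last 18 weeks (12/18 = 67%). None is in the standard period.

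**3. What a week without a class costs.** The logs are weekly records, and nothing says a late one is refused. A participant still attending can hand it in at the next class, about 2 or 4 weeks later. The cost is timeliness, with a risk of entries filled in from memory. For someone who has stopped attending there is no next class, so no stated route exists in either period.

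**4. What the interviews cover.** Three one-week recalls are planned. Weeks 12 and 26 fall inside the 36 log weeks, and week 52 comes after the logs end. Only week 26 lies within the 24 maintenance weeks. This gives a check at single time points, not a weekly series.

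**5. Direction and size of the error.** The documents give neither a log-return rate nor a practice rate for non-returners, so both are assumed here. Let r be the share of log weeks returned (assumed 60% to 90%), k the practice of non-returners relative to returners (assumed 0 to 1), and m the returners' mean.

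- True mean over all randomised = m × [r + (1 − r) × k]
- Error if only returned logs are averaged = 1 / [r + (1 − r) × k] − 1
- Error if unreturned logs count as zero = r / [r + (1 − r) × k] − 1

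| r | k | Returned logs only | Unreturned = zero |
|---|---|---|---|
| 0.6 | 0 | +66.7% | 0% |
| 0.6 | 0.5 | +25.0% | −25.0% |
| 0.6 | 1 | 0% | −40.0% |
| 0.8 | 0 | +25.0% | 0% |
| 0.8 | 0.5 | +11.1% | −11.1% |
| 0.8 | 1 | 0% | −20.0% |
| 0.9 | 0.5 | +5.3% | −5.3% |
| 0.9 | 1 | 0% | −10.0% |

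Worked line, r = 0.8 and k = 0.5: 0.8 + 0.2 × 0.5 = 0.9; 1/0.9 − 1 = +11.1%; 0.8/0.9 − 1 = −11.1%.

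The count in step 2 does not enter these formulas. A week without a class affects r only to the extent that late logs are never handed in.

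**The case against.** The strongest reply is that the interview questions already measure days and minutes of practice without relying on attendance. The Protocol says this method has worked well before, but claims only moderate success for logs. Section 8 encourages people who stop the intervention to complete the remaining assessments. Staff record attendance at every class, so non-attenders stay visible. The quality-assurance file in 10.3.3 already tracks receipt of logs. The study is descriptive, and its only numeric feasibility criterion is 80% follow-up.

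Much of this stands. A reader might infer that a third of the log data will be lost; the documents do not support that, because a log from a week without a class can be returned at the next one. A reader might also infer that home practice will be overstated and the verdict tilted towards feasibility. That would require averaging over returned logs only and non-returners practising less, and the documents state neither. No go/no-go threshold is tied to log-based practice.

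The reply does not close two gaps. One recalled week out of 24 cannot supply weekly practice through the taper. And tracking receipt of logs does not say how unreturned ones enter the summary.

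**Conclusion.** The point holds as a problem of selective missing data. Log return is tied to attendance in both periods, and weekly hand-in cannot be followed in 12 of 24 maintenance weeks (12 of 36 log weeks, none in the standard period). For continuing attenders the taper causes delay and some recall risk; for those who stop attending, the logs have no stated way back.

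Overstatement is likely only if the mean uses returned logs and non-returners practise less. Under the assumed ranges (60% to 90% of log weeks returned, non-returners practising at 0 to 100% of the returners' level), the error lies between 0% and +67% for returned logs only, and between 0% and −40% if unreturned logs count as zero. These figures show how far the unstated rule could move the result; they do not predict it. The count of class weeks rests on the documents alone. The design can stand, but the log-based home-practice outcome needs a return route outside class and a stated analysis rule before it can be interpreted.

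**What to change.** **Collection (Protocol 5.1.6.iv, with Section 3 and Table 4 aligned).** Ask participants to return all completed weekly logs at the next class, by mail, or at the 12-, 26- or 52-week visit. Use a contact the plan already makes ("Participants will receive a reminder call before the first class and whenever they miss any classes", 5.1.6.ii) to ask about that week's days and minutes of practice. The call helps with non-attenders; it does nothing for weeks in which no class is held, which the other routes must cover.

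**Analysis (Protocol 9.6.i and SAP).** Summarise home practice over all participants randomised to Tai Chi. Report the percentage of expected logs returned, by period and by attendance, building on the receipt tracking in 10.3.3. Show the prior-week interview data alongside. Add a sensitivity analysis that counts unreturned weeks as zero, labelled as a lower bound.

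**Cost.** Wording changes in both documents, prepaid envelopes, and one or two questions in an existing call. Weeks recalled by phone are less precise than logs, and reported adherence may look lower.
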